Objectives	The primary objective of this study is to show that, when used before, during, and after an EP procedure, CoVa™ 2 is able to successfully measure vital signs, waveforms, and hemodynamic parameters from patients, indicate the efficacy of the EP procedure, and show any signs of patient decompensation or complications. An additional objective of this study is to show that, through use of CoVa™ 2, patients can be discharged relatively early from the hospital after undergoing an EP procedure.
Methodology	No randomization or blinding methods will be used for this study.
Endpoint	The primary endpoint will be if at least 50% of subjects studied in this trial are able to be discharged relatively early from the hospital if they are monitored with CoVa™ 2. A detailed retrospective statistical report will be the determining factor in meeting this success criteria.
Study Duration	Approximately 6 months
Participant Duration	Up to 7 days (until hospital discharge).
Duration of IP administration	N/A
Population	Approximate sample size: 20 subjects. Subjects are those which need an EP procedure,, including atrial fibrillation and SVT, pacemaker or ICD implant.
Study Sites	NYU Medical Center Electrophysiology [name]
Number of participants	20 subjects across one site

Description of Study Agent/Procedure	Subjects will be measured with CoVa™ 2 before and after an EP procedure.
Reference Therapy	N/A
Key Procedures	EP
Statistical Analysis	Statistical comparison (e.g. correlations) of measurements made before, during, and after the EP procedure to prove or disprove the above-mentioned study hypothesis.

Schematic of Study Design

1 Key Roles

Principle Investigator
[name]
[contact]

Sub Investigator
[name]
[contact]

Introduction, Background Information and Scientific Rationale

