Current hospital monitoring typically involves manually measuring conventional vital signs—such as blood pressure, heart rate, respiration rate, temperature, and pulse oximetry—initially every 15 minutes and then every few hours. This entire suite of vital signs is necessary, as it is rare that a single parameter can predict patient decompensation; more often, especially with complex disease states, all the vital signs (and often even more parameters) are required. And while not overly complicated, this process can be time consuming and inefficient. A clinician (typically a nurse, although increasingly someone with less training) enters the patient's room, straps to the patient a blood pressure cuff (around the brachium), an oximeter (on the finger), a thermometer (in the ear), and sometimes ECG leads (affixed to the chest), takes a series of

measurements, and then removes these sensors. The entire process takes about 5-10 minutes. Often measurement values are simply written down and transcribed later. Moreover, measurement of more sophisticated parameters, or measurements made outside of the hospital, are rarely done. In the hospital setting, parameters like stroke volume and cardiac output are typically only made with highly invasive or complicated devices requiring specialty-trained technicians, such as a pulmonary-arterial catheter or Doppler ultrasound machine. Patients are almost never discharged early and measured in the home, as the devices and infrastructure to enact such protocols do not exist. The sensor used in this clinical trial, is a low-cost, easy-to-use, body-worn system that cures the deficiencies listed above. It will ultimately measure all vital signs, along with stroke volume, cardiac output, and fluids, non-invasively and from a single location on the patient's body. This sensor can be coupled to a cloud-based system for data analytics that generates timely, actionable information for clinical staff regardless of patient setting (e.g. in either the home or hospital). With such a system, patients could be discharged early or monitored at home to prevent readmissions. This may improve patient outcomes, since delays in recognition of a change in status often lead toward longer hospital stays and, in some cases, patient morbidity and mortality.

Name and Description of the Investigational Agent

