In addition to the primary study objective, investigate the following questions: 1) can measurements made by the CoVa™ 2 (particularly stroke volume (SV), cardiac output (CO), fluid status, arrhythmia detection, and basic vital signs) be successfully made before, during, and after an EP procedure?; 2) is there correlation between CoVa™ 2-measured parameters (particularly volume status, heart rate and arrhythmia, SV, and CO) before, during, and after an EP procedure?; 3) does RF ablation during an EP procedure interfere with CoVa™ 2 measurements?; 4) does a 200-300 Joule shock during a DC cardioversion procedure interfere with CoVa™ 2 measurements?; and 5) is the CoVa™ 2's usability suitable for hospital clinicians?

Description of Study Design

Study subjects scheduled for an EP procedure who have signed an informed consent form (ICF) will be admitted to the study. Prior to the EP procedure (e.g. in a hospital room or operating room at NYU Medical Center), an employee of NYU will prep the subject's skin with an alcohol wipe, apply the CoVa™ 2 Sensor using a pair of disposable electrodes, connect it to the Gateway Device using Bluetooth®, and ensure that it is transmitting information from the CoVa™ 2 Sensor through the Gateway Device to the Cloud-based System. All transmitted information will be de-identified. All subjects will continue to be monitored with standard of care equipment.

Once this data pathway is verified, measurements will be made from the subject for a period of approximately 2 hours prior to the EP procedure. More specifically, measurements will be made continuously for a period of about 90 seconds, and then, as described above, information will be transferred from the CoVa™ 2 to the Gateway Device, and from the Gateway Device to the Cloud-based System. This process will take roughly 120 seconds. Once it is complete, this 'duty cycle' will be repeated for the duration of the 2-hour period, i.e. measurements will again commence for a period of about 90 seconds, and then paused for about 120 seconds while data is wirelessly transmitted as described above.

Measurements will be temporarily halted as the subject is moved into the operating room and prepped for the EP procedure. Prior to the procedure, the CoVa™ 2 sensor will be attached to an external power supply as described above. Once the procedure is started, measurements will be made in the same manner as described above.

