Once the EP procedure is complete, the subject will be transferred from the operating room to a hospital room, where they will stay overnight. Measurements will be made during this period, but not while the subject is being transferred. Once the subject is situated in the hospital room, the CoVa™ 2 Sensor will be applied to the subject and connected to the external power supply in the same manner as described above. Then measurements will commence according to the same duty cycle as described above.

The patient will continuously wear the CoVa™ 2 system until they are discharged for a period of about 24 hours. During this period, data from the sensor will be sent to the Gateway and Cloud-based System, and then analyzed retrospectively.

During the course of the study, scientists at toSense will use the Data Analytics Software to process measurement information from CoVa™ 2, with a focus of proving or disproving the study's primary hypothesis, i.e. when the CoVa™ 2 Sensor is used before, during, and after an EP procedure, can it successfully measure patients, indicate the efficacy of the EP procedure, show any signs of patient decompensation or complications, and allow a patient to be discharged relatively early?

More detailed analyses will investigate the study's secondary objectives, i.e.: 1) can measurements made by the CoVa™ 2 Sensor be successfully made before, during, and after an EP procedure; 2) is there correlation between parameters such as volume status, heart rate and arrhythmia, SV, and CO before, during, and after an EP procedure; 3) does RF ablation during an EP procedure interfere with CoVa™ 2 Sensor measurements?; 4) does a shock during a DC cardioversion interfere with CoVa™ 2 Sensor measurements?; and 5) is the usability of the CoVa™ 2 Sensor adequate before, during, and after an EP procedure suitable for clinicians?

Upon completion of the study, a report will be drafted describing the above-described information. The report may evolve into a peer-reviewed publication if this is determined by the PI to be an appropriate course of action.

This measurement protocol will be performed for a period of at approximately 6 months.

Study Endpoints

Primary Study Endpoints

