The primary endpoint will be if at least 50% of subjects studied in this trial are able to be discharged relatively early from the hospital if they are monitored with CoVa™ 2, as determined through a retrospective analysis. A detailed retrospective statistical report will be the determining factor in meeting this success criteria.

Study Enrollment and Withdrawal

Inclusion Criteria

In order to be eligible to participate in this study, an individual must meet all of the following criteria:

1. Patients with arrhythmias and other cardiac conditions that are scheduled for EP procedures.
2. Subject is over 22 years of age at the time of consenting
3. Subject and/or legally authorized representative is willing to undergo the informed consent process prior to enrollment in the study

Exclusion Criteria

An individual who meets any of the following criteria will be excluded from participation in this study:

1. Pregnant subjects
2. Subjects who are participating in another clinical study that may affect the results of either study

3. Subjects who are unwilling or unable to wear the sensor (and electrodes) for a period of up to 14 hours
4. Subjects who are considered by the principle investigator to be medically unsuitable for study participation

Vulnerable Subjects

Vulnerable subjects will not be utilized in this study. In the case of a vulnerable population patient being identified; they will not be included in the study or analysis..

Strategies for Recruitment and Retention

No NYULMC media will be used to recruit subjects. Subjects that are scheduled for an EP procedure and meet the inclusion criteria will be approached for enrollment.

Subjects will be consented in a quiet and private environment. Subjects will be given the opportunity to take the written consent form home to review overnight.

Use of DataCore/Epic Information for Recruitment Purposes

This study will utilize EPIC to identify subjects. Once potential subjects have been identified, the study team will notify the treating physician (TP) that they have patients eligible to participate. The study team will obtain approval from the treating physician to approach the eligible patient for the study.

Duration of Study Participation

The total duration of study participation is about 1.5 days. This includes:

Written Informed Consent Process: 1 day

Study Procedure: 1 day

Measurement prior to EP Procedure: 1-3 hours

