The PI will confirm prior to enrollment that each subject qualifies for the study. The eligible subject will be approached by the research team. All patients willing to participate will personally sign and date the latest IRB approved version of the consent form. Written and verbal versions of the participant information and informed consent will be presented to the participants detailing no less than: the exact nature of the study; the implications and constraints of the protocol; the known side effects and any risks involved in taking part. It will be clearly stated that the participant is free to withdraw from the study at any time for any reason without prejudice to future care, and with no obligation to give the reason for withdrawal. The participant will be allowed as much time as wished to consider the information, and the opportunity to question the Investigator, their general practitioner or other independent parties to decide whether they will participate in the study. Written Informed Consent will then be obtained by means of participant dated signature and dated signature of the person who presented and obtained the informed consent. A copy of the signed Informed Consent will be given to the participants. The original signed form will be retained at the study site, in a research binder maintained by the study team in a locked cabinet. All documents will be stored safely in confidential conditions. On all physical and electronic study-specific documents, other than the signed consent, the participant will be referred to by a study participant number/code, not by name.

Visit 2 (Day of EP procedure)

- Ensure the subject has no additional questions regarding the study
- Once the subject has been prepped for surgery, apply the sensor to the subject's upper chest using the toSense approved electrodes
- Connect the device to the power source
- Study participant will be assigned a study number/code

- All data transmitted by the CoVa2 device will be de-identified.
- Run several test measurements on the sensor to ensure that the device is actively measuring on the subject
- Explain to the subject that the sensor will measure for a 90 seconds period, with 120 second pause in between measurements
- Measurements will not be made while the subject is transferred to and from the surgery room
- Measurements will be made until the patient is discharged

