- Immediately prior to discharge, a study team member will remove the CoVa™ 2 device from the patient, and ensure a final data transmission.

Withdrawal/Early Termination Visit

If the subject withdraws from the study:

- A reasonable attempt should be made to find out why the subject dropped out of the study
- Subjects may be replaced in the study
- Record the whether the withdrawal was from either the subject or principle investigator

Ethics/Protection of Human Subjects

Ethical Standard

The investigator will ensure that this study is conducted in full conformity with Regulations for the Protection of Human Subjects of Research codified in 45 CFR Part 46, 21 CFR Part 50, 21 CFR Part 56, and/or the ICH E6.

Institutional Review Board

The protocol, informed consent form(s), recruitment materials, and all participant materials will be submitted to the IRB for review and approval. Approval of both the protocol and the consent form must be obtained before any participant is enrolled. Any amendment to the protocol will require review and approval by the IRB before the changes are implemented to the study. All changes to the consent form will be IRB approved; a determination will be made regarding whether previously consented participants need to be re-consented.

Informed Consent Process

Consent/Accent and Other Informational Documents Provided to Participants

Consent forms describing in detail the study procedures, and risks are given to the participant and written documentation of informed consent is required prior to starting intervention/administering study product. The following consent materials are submitted with this protocol:

- Informed Consent Form

Consent Procedures and Documentation

Informed consent is a process that is initiated prior to the individual's agreeing to participate in the study and continues throughout the individual's study participation. Extensive discussion of risks and possible benefits of participation will be provided to the participants and their families. Consent forms will be IRB-approved and the participant will be asked to read and review the document. The investigator will explain the research study to the participant and answer any questions that may arise. All participants will receive a verbal explanation in terms suited to their

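### A single-group proportion of at least 50% cannot show that CoVa 2 enables early discharge, nor, alone, that the early-discharge calls were correct

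*Protocol*

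**What the plan says.** **Criterion.** Under Primary Study Endpoints, and in the Endpoint row of the Protocol Summary, the trial succeeds if at least 50% of subjects "are able to be discharged relatively early from the hospital if they are monitored with CoVa™ 2, as determined through a retrospective analysis". A retrospective statistical report decides whether this is met. About 20 evaluable subjects are planned.

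**Aim.** The Objectives row of the Protocol Summary sets out to show that, "through use of CoVa™ 2, patients can be discharged relatively early from the hospital after undergoing an EP procedure". The Primary Objective section asks whether CoVa data can allow early discharge with monitoring at home. Description of Study Design makes early discharge part of the primary hypothesis to be proved or disproved.

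**Conduct.** The Protocol Summary gives no randomization or blinding and lists the reference therapy as not applicable. Description of Study Design states: "All subjects will continue to be monitored with standard of care equipment". After the procedure, "the subject will be transferred from the operating room to a hospital room, where they will stay overnight". In that period, "data from the sensor will be sent to the Gateway and Cloud-based System, and then analyzed retrospectively".

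**End of observation.** For Visit 2: "Measurements will be made until the patient is discharged", and "Immediately prior to discharge, a study team member will remove the CoVa™ 2 device from the patient". Duration of Study Participation adds only that a follow-up interview may take place.

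**Benefit statement.** Known Potential Benefits tells the reader that subjects may leave hospital earlier because of the extra monitoring.

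**The concern.** The aim attributes early discharge to the device, while the criterion is one proportion in one group. That proportion counts together subjects who would have been called fit to leave on routine monitoring and any whom CoVa data made it possible to call fit. Nothing in the protocol separates them.

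The protocol also describes no step that sets a subject's classification against what then happened in hospital. So even a reader interested only in whether CoVa monitoring is good enough to support early discharge learns how many subjects were called dischargeable, not whether those calls were sound.

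The report may become a peer-reviewed publication. A pass could then be presented as evidence that CoVa 2 makes early discharge possible, which the design does not establish.

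**Working it through.** **1. The plan's own figure.** The protocol gives no assumed rate, reference rate, error level or power from which 20 subjects or the 50% threshold could be derived, so there is nothing to reproduce. The threshold is 0.50 × 20 = 10 subjects.

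**2. What would be needed, and what is described.**

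| Needed | In the protocol |
|---|---|
| Attribution: a comparator or reference rate | One group; reference therapy not applicable; no rate given |
| Attribution: an assessment without CoVa data | None described; the named comparison is of measurements before, during and after the procedure |
| Sufficiency: calls checked against later events | No link described, although all subjects stay overnight under routine monitoring |
| Home monitoring: data after discharge | Sensor removed immediately before discharge; interview optional and undefined |

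**3. Chance of passing if CoVa adds nothing.** Let *p* be the share who would be called fit to leave anyway. The documents give no value, so *p* is an assumed range.

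P(X ≥ 10) = Σ (k = 10 to 20) C(20, k) p^k (1 − p)^(20 − k)

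| Assumed *p* | P(at least 10 of 20) |
|---|---|
| 20% | 0.003 |
| 30% | 0.05 |
| 40% | 0.24 |
| 50% | 0.59 |
| 60% | 0.87 |
| 70% | 0.98 |

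If the total share is background plus a CoVa contribution, then 60% + 0 points and 30% + 30 points both total 60% and both pass with probability 0.87. This follows from the totals being equal; it shows only that the criterion sees the total.

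**4. A miss.** P(X ≤ 9) at a total share of 60% is 1 − 0.8725 = 0.13, and at 70% it is 1 − 0.9829 = 0.02. A miss therefore does speak against a high share.

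**5. Precision.** The exact (Clopper-Pearson) 95% limits are the 0.025 quantile of Beta(x, n − x + 1) and the 0.975 quantile of Beta(x + 1, n − x).

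- 10/20: 27.2% to 72.8%.
- 0/10, for example no complications among ten subjects called dischargeable: the upper limit is 1 − 0.025^(1/10) = 30.8%, so 0% to 30.8%.

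**The case against.** **The question may be sufficiency, not added effect.** The endpoint is conditional on CoVa monitoring, and the Primary Objective asks what CoVa data can allow. The Introduction names missing devices and infrastructure as the barrier: "Patients are almost never discharged early and measured in the home, as the devices and infrastructure to enact such protocols do not exist". On that reading, subjects fit to leave anyway do not contaminate the result, and no assessment without CoVa is needed. This stands as a legitimate reading. What remains under it is that the calls are not checked against events before actual discharge.

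**The Introduction might be taken as a near-zero benchmark.** It does not serve as one. It is qualitative and concerns actual early discharge with home measurement, whereas the endpoint is assessed fitness to leave.

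**A statistical analysis plan may fill the gaps.** It may define early discharge, say how ability is assessed, or add an interval or a check against complications. The primary objective already includes showing signs of decompensation or complications, so such a check would be within scope. But the success criterion is protocol text, and defining its terms leaves it an uncontrolled proportion.

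**The study is introductory.** A reader might infer that the single group is itself an error. It is not: the design is openly declared and suits an introductory study. The fault is the mismatch between what the criterion measures and what the objective claims.

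**Conclusion.** The point holds in a limited form. Meeting the 50% criterion cannot show that early discharge is achieved through CoVa 2. On the sufficiency reading, the proportion alone does not show that the calls were correct. Both conclusions rest on the protocol's text and do not depend on the binomial figures.

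The size of the problem is not known. A reader might infer from 0.59 or 0.87 that a pass is likely without any device contribution. The documents do not support that, because they give no background share. At an assumed 20% or 30% the chance is 0.003 or 0.05, and a pass would then point to something beyond background. Nor is the criterion empty: a miss carries some information.

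Two related limits follow from the text. The home-monitoring part of the primary question is not observed. The benefit statement also sits uneasily with the study design, which describes no use of CoVa data in discharge decisions. This is a separate consistency point that needs reconciling; it does not bear on the argument about the proportion.

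**What to change.** 1. **Wording.** In the Protocol Summary and Primary Study Endpoints, report the proportion descriptively with its exact 95% CI. State that it does not show that CoVa 2 enables early discharge, and limit the conclusion to in-hospital monitoring.
2. **A check of the calls, for analysis only and with no effect on actual discharge.** Pre-specify one post-procedure time. Classify each subject from CoVa data up to that time and lock the classification before later data are opened. Count unusable CoVa data as non-success. Tabulate both kinds of call (dischargeable, not dischargeable) against complications in the routine record from that time to actual discharge, with exact intervals.
3. **Consistency.** Reconcile Known Potential Benefits with the retrospective use of CoVa data in Description of Study Design.

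Having one assessor read each record first without and then with CoVa data is not required. The fixed order invites anchoring, so any such reading should be labelled exploratory.

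**Cost.** No added subjects or procedures are needed. Step 2 requires modest record abstraction for about 20 subjects and linkage by study code to the de-identified CoVa data. That means an IRB-approved amendment and a check that the HIPAA authorization covers it. The headline becomes less favourable and the intervals will be wide. If few complications occur, the table will describe rather than prove.

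### The primary endpoint's 'relatively early' discharge has no clock time and no data cut-off, so the call can draw on later data and 'early' can be set after the course is known

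*Protocol*

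**What the plan says.** The protocol's section on primary endpoints sets this criterion: "The primary endpoint will be if at least 50% of subjects studied in this trial are able to be discharged relatively early from the hospital". The rest of that sentence makes CoVa 2 monitoring a condition, and the section names how the matter is settled: "as determined through a retrospective analysis. A detailed retrospective statistical report will be the determining factor in meeting this success criteria". The Endpoint row of the Protocol Summary repeats the criterion and the role of the report.

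Protocol, Description of Study Design: after the procedure "the subject will be transferred from the operating room to a hospital room, where they will stay overnight". On recording: "The patient will continuously wear the CoVa™ 2 system until they are discharged for a period of about 24 hours". On analysis: "During this period, data from the sensor will be sent to the Gateway and Cloud-based System, and then analyzed retrospectively". The same section keeps every subject on standard monitoring, and states that "scientists at toSense will use the Data Analytics Software to process measurement information from CoVa™ 2" while the study is running. The Methodology row of the Protocol Summary rules out randomization and blinding.

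The term 'relatively early' appears in the Protocol Summary, Primary Objective, Description of Study Design and Primary Study Endpoints. None of these gives an hour, a usual discharge time or a reference stay.

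**The concern.** No subject's discharge is scheduled by the device. Whether a subject could have left early is therefore a hypothetical judgement, made afterwards from a record that runs to actual discharge. Two things are left open.

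- **Data window.** A real early-discharge decision is made without knowing what follows. The protocol sets no cut-off that would put the retrospective judgement in the same position, so later data may inform it.
- **Time.** Any moment before actual discharge could be called 'relatively early', and nothing requires it to be fixed before the data are seen.

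At stake is the meaning of the only primary success criterion. A reported rate of 50% or more might describe what the CoVa data supported when the decision was due. It might instead describe how many subjects turned out to have an uneventful stay. The wording does not separate the two. Adding a comparator or a reference rate would leave both gaps in place.

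**Working it through.** **Figure to reproduce.** None. The protocol gives no null rate, expected rate, error level or power behind the 50% threshold or the 20 subjects. The check is how the stated rule behaves.

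**Inputs.**
- Threshold: at least 50% (Primary Study Endpoints).
- n = 20 evaluable subjects (Total Number of Participants and Sites). Passing therefore needs 0.5 × 20 = 10 or more.
- p, the true share judged dischargeable early: not in the protocol, so a range is assumed. Subjects are taken as independent.

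**Step 1: pass probability.** P(X ≥ 10) = Σ from k = 10 to 20 of C(20,k) p^k (1−p)^(20−k).

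| Assumed p | P(at least 10 of 20) |
|---|---|
| 30% | 0.048 |
| 40% | 0.245 |
| 50% | 0.588 |
| 60% | 0.873 |
| 70% | 0.983 |
| 80% | 0.9994 |
| 90% | >0.9999 |

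Hand check at p = 0.5: C(20,10)/2^20 = 184756/1048576 = 0.1762, and by symmetry (1 + 0.1762)/2 = 0.588.

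**Step 2: how the choice of time moves p.** As an illustration only, suppose each subject's earliest suitable time is spread evenly over a 24-hour stay. If 'early' means h hours before actual discharge, then p = 1 − h/24.

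| h | p | P(at least 10 of 20) |
|---|---|---|
| 2 | 22/24 = 92% | about 1.00 |
| 12 | 12/24 = 50% | 0.59 |
| 18 | 6/24 = 25% | 0.01 |

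With the patients and the threshold unchanged, the result runs from near-certain pass to near-certain fail on the choice of h alone. The even spread is an assumption; what carries over is that p depends on an hour the protocol does not set.

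**Step 3: what hindsight would do.** If a subject with an uneventful stay were scored a success because the stay was uneventful, p would equal the share of uneventful stays. At 70% or more, Step 1 gives a failure probability of at most 1 − 0.983 = 0.017, with or without information from the device.

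**Step 4: is a landmark alone enough?** Suppose success means a 'yes' at the landmark and no event afterwards, but the 'yes' follows no fixed CoVa rule. An assessor who says 'yes' to everyone then scores the share uneventful after the landmark. That share is at least as large as the share uneventful throughout, so the pass probabilities are no lower than in Step 3. The remedy therefore also needs a CoVa-based rule set in advance, and a display that exposes an all-'yes' rule.

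**The case against.** The strongest reply is that retrospective means only after collection. A retrospective analysis can replay each record up to a cut-off, and a statistical analysis plan, not available here, may set one. This stands in part: look-ahead is permitted by the wording, not stated by it. It does not dispose of the point, because the protocol itself fixes the endpoint and makes an after-the-fact report its judge, without tying that report to a rule set beforehand.

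Three stronger readings are tempting, and the document does not support them.

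- **That CoVa data play no part in the call.** The endpoint is conditioned on monitoring with CoVa 2, and Description of Study Design has the analysis process CoVa measurements to look for signs of deterioration. The judgement is linked to device data. What is missing is a reading or threshold that defines 'able to be discharged'.
- **That the criterion can hardly fail.** This depends on an uneventful-stay rate the protocol does not give. At 30% the pass probability is 0.05 and at 50% it is 0.59.
- **That the protocol offers conflicting reference stays.** Overnight and about 24 hours agree. The 7 days in the Participant Duration row is a ceiling on participation, not a reference for 'early'.

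It is also fair that this is an introductory, single-site study in which standard monitoring continues for all. The harm is to interpretation of the primary result.

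**Conclusion.** The concern holds in this form: 'relatively early' is tied to no hour, and nothing limits the judgement to data available at the would-be discharge time. The sole primary success criterion can therefore be settled after the course is known. The absence of a time and of a cut-off is plain in the text; actual use of later data is a possibility the text leaves open.

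The size is conditional on an unstated share. Across assumed shares of 30% to 80% the pass probability runs from 0.05 to above 0.99. Only if most stays are uneventful is a pass likely regardless of what CoVa contributes. This should be settled before any data are analysed.

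One related passage needs reconciling: Known Potential Benefits says subjects may leave hospital sooner because of the monitoring, which sits badly with an overnight stay and a retrospective analysis. It does not supply the missing definition.

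**What to change.** Amend Primary Study Endpoints and the matching Protocol Summary row, before any data are analysed, as follows.

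1. State one landmark, in hours after the procedure, and a yes/no classification rule based on CoVa data. The investigators choose both.
2. Apply the rule only to each subject's CoVa record up to the landmark, and lock the call before later data are opened.
3. Count a success only if the call is 'yes' and the existing chart shows no pre-defined complication or unplanned intervention from the landmark to actual discharge. The investigators define these events in advance.
4. Apply the 50% rule to that count.
5. Report the cross-table of calls by later events, so that a rule that says 'yes' to everyone is visible.

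Cost: protocol wording, a truncated data extract per subject, some chart abstraction against a written event definition, and an arrangement that keeps later data from whoever makes the call. The last needs care because the device provider's scientists process data during the study. No extra patients or procedures are needed. The reported success rate may be lower.
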